## **8. SAFETY ASSESSMENTS**

All data derived from this study is for research purposes only. Subjects will be monitored at all times for adverse events.

### **8.1 Potential Risks**

The proposed study will utilize widely used and approved procedures including: commonly used neuropsychological questionnaires and interview materials, blood pressure measurements, brain MRI, carotid ultrasound, and blood draws. Neuropsychological assessment may be accompanied by anxiety, frustration and overall fatigue. The attachment and removal of a blood pressure cuff, cuffs for venous occlusion, and ultrasound probe on the neck may cause mild discomfort. Brain imaging requires the participant to stay still and lie down for 50-60 minutes, which may cause boredom and minimal reversible back pain. Because of the closed space and noise, undergoing an MRI may be associated with anxiety or panic reactions. Claustrophobic-prone individuals will not be asked to undergo the MRI portion. We will ask participants to breathe via a mask air richer in CO2 than normal atmospheric air (5-8%) during the brain MRI procedure. The CO2 reactivity procedures were well tolerated by elderly subjects in our prior studies, and have been performed numerous times in our laboratory without complications. The reported potential side effects may include a feeling of dizziness, faintness, or anxiety during CO2 inhalation.

The discontinuation of blood pressure medications may be associated with a risk of marked blood pressure elevation and development of associated neurological or cardiac symptoms: headaches, dizziness, blurred vision, chest pain or ischemic neurological events. In our pilot study, none of the participants experienced these symptoms. To minimize this risk, medications will be slowly tapered over a 2-4 week period while study personnel carefully monitor subjects.

The proposed study will utilize drugs approved by the Food and Drug Administration for the treatment of hypertension. They are well tolerated by young and elderly individuals and have been used extensively in

clinical practice. Possible side effects include: dizziness, cough (lisinopril), weakness, fatigue, lower extremity edema and constipation (amlodipine), and hypotension. Renal failure and hyperkalemia are also potential complications of candesartan and lisinopril. HCTZ may cause renal failure, volume depletion, and hypokalemia. Lisinopril may cause a dry cough and angioedema. Beta blockers may be associated with weakness and bradycardia. Adverse events will be queried at each visit. Alternatives to antihypertensive medications include no therapy, which is not safe or ethical in patients with hypertension. Drug-drug interaction will be assessed by the study physician. If there is contraindication to use the candesartan or lisinopril and one of the other participant's medications then he/she will not be able to enroll in the study. If the contraindication is between an add-on agent (amlodipine, metoprolol, or HCTZ) then the participant will be enrolled but we will avoid using that agent as an add-on as described in section 5.3. Use of lithium is a contraindication for both lisinopril and candesartan and hence lithium users are excluded. The following combinations of medications are contraindicated for the add-on drugs: Simvastatin >20 mg with amlodipine, reserpine with metoprolol, and clonidine with metoprolol.

## 8.2 Specification of Safety Parameters

The study medications may lead to adverse drug reactions (rash, edema, and in severe cases anaphylaxis) and uncomfortable side effects. If this occurs, the study medication will be discontinued and the subject's primary care provider notified. If the subject cannot tolerate the study medication, the study medication will be stopped and he/she will be referred to their primary care physician for ongoing hypertension treatment. The participant will however be continued in the study and asked to undergo the final visit evaluations. Subjects will be monitored carefully for symptoms, blood pressure control, and blood chemistry abnormalities during treatment, as described in the methods section above. A physician (PI) and trained personnel will be available at all times to respond to subjects' concerns. In the event of an emergency, resuscitation equipment is readily available in all the research areas where subjects are evaluated. Antihypertensive medications will also be adjusted up/down to maintain blood pressure below 140/90 mm Hg and above 100/45 mm Hg or at the discretion of the study physician for maintaining safety. For example, if blood pressure readings are high at their study visits but normal/low at home or the subject reports orthostatic dizziness the clinician will use his judgment to change the dosage of the study meds.

The subject's primary care physician will be informed of study plans. Frequent monitoring will include visits, blood pressure checks, laboratory testing and phone contact. Blood testing for kidney function and electrolytes (potassium) will be performed at baseline, 1, 3, 6 and 12 months. If needed, additional calls, visits, or laboratory testing will be conducted as decided by the PI and /or the primary care physician. If symptoms develop during any of the evaluations, procedures will be terminated immediately. The experimental procedures will be conducted in a well-supervised facility and subjects will be under constant observation by skilled professionals. Those who could not continue on the study medications will be asked to return for collection of outcome measure if they agree to return for the final assessment visit.

(i) **CO2 Administration**: CO2 will be given via mask connected to a tank at a concentration of 5-8% and will be mixed with air and/or oxygen and nitrogen. To minimize respiratory discomfort, CO2 breathing intervals will be kept as short as possible to achieve desired increase in ETCO2 and will never exceed 2 minutes in length (continuous 2-minutes or two 1-minute blocks interspaced with 1-minute off). Heart rate, blood pressure, oxygen levels, and ETCO2 will be continuously and non-invasively monitored in order to limit risk for insufficient oxygenation, hypertension, and significant distress. In addition, the MR gantry is equipped with a camera/Glass window allowing continuous monitoring of the subjects from the MR control room; subjects are given a pneumatic bulb that starts off an alarm in the control room in case of emergency. CO2 administration will be promptly terminated if any of the following conditions occur: any complaint of subject discomfort, appearance of new neurologic symptom, systolic blood pressure increase of >50-55 mmHg or mean arterial blood pressure increase of >35-40 mmHg over normo-capnic levels, or pulse acceleration over baseline of 30-40 beats per minute. To further minimize risk of complications, subjects with **active asthma or chronic obstructive pulmonary disease, will not be given CO2**.

(ii) **Neuroimaging**: Should subjects feel discomfort during the MRI procedure the experiment will be terminated upon their request. The operators of the MRI scanner will take steps such as using foam pads when necessary to minimize the risk of excessive heating or burns from contact with the MRI transmitting and

receiving coil or conductive materials. Subjects will be screened for magnetic material before each study, per the standard of care at the MRI suite. Patients with pacemakers, aneurysm clips, metallic prostheses or shrapnel fragments are at risk at an MR environment and will be excluded from the neuroimaging portion of the study. Women of childbearing age will not be included. Earplugs or close fitting silicon padded headphones will be provided to protect from damage to the inner ear due to the loud tone produced by the MRI scanner. Subjects will be observed and monitored at all times by the operators, and can be moved out of the machine at their request. Subjects will be able to communicate through an intercom with the physician/scientist or technician at all times. In addition the MR gantry is equipped with a camera allowing continuous monitoring of the subjects from the MR control room; subjects are given a pneumatic bulb that starts off an alarm in the control room in case of emergency. All people entering the exam room where the magnet is located will be screened for magnetic material before entering the room. This will apply to subjects, experimenters, and staff.

(iii) **Incident dementia:** Although limited information is available, it is estimated that the yearly conversion rate is close to 7% in executive MCI. We will screen at each visit for any new diagnosis related to cognition (dementia, delirium, others), new medication started (cholinesterase inhibitors or memantine), or proxy/self-report of new diagnosis of dementia. The physician (PI) will review the clinical history with the study neurologist ([name]) and a consensus diagnosis will be made. We will compare the number of people who develop incident clinical dementia in both groups as part of our safety analyses.

### 8.3 Antihypertensive replacement protocol

Those with hypertension who are receiving antihypertensive medications will have their current medications tapered gradually using an established protocol that has minimal risk. Their primary care provider will also be notified, if the participant agrees, before initiating any changes in the participant’s blood pressure medications. If the subject agrees then a letter will be faxed or mailed to their primary care physician providing information about contacting the study personnel regarding any concerns or comments about the antihypertensive replacement. Participants will be provided with an automated blood pressure monitor and a blood pressure diary (Home Blood Pressure Monitoring Flow Sheet) to monitor their blood pressures at home. Contact by the study personnel will be weekly, or more if needed, for review of blood pressures. Once the participant is off all antihypertensive medications, he or she will undergo the baseline evaluation. The following protocol will be used for the withdrawal:

1- All participants will receive personalized written instructions on tapering and discontinuation of antihypertensive medications, description of symptoms associated with possible adverse events and familiarization with the study protocol (Home Blood Pressure Monitoring Flow Sheet). They will be instructed to share this information with their spouses or other members of their households. The timeline for medication tapering is summarized in the following table:

Number of antihypertensive meds	Week 1	Week 2	Week 3	Week 4
	Day 0-7	Day 8-14	Day 15-21	Day 22-28
One antihypertensive med	Half weekly dose	No meds Baseline Visit		
2 antihypertensive meds	Half weekly dose med 1 Full weekly dose med 2	No med 1 Half weekly dose med 2		
3 antihypertensive meds	Half weekly dose med 1 Full weekly dose med 2 and 3	No med 1 Half weekly dose med 2 Full weekly dose med 3	No med 1 and 2 Half weekly dose med 3	No Meds Baseline visit

2- Subjects and/or proxy will be provided with a portable automated blood pressure (BP) monitor and a diary to take home. They will be asked to measure BP 2x times a day (morning and before sleep) and record into a diary.

3-Daily/weekly dose reduction are shown in the Table above. Baseline visit will performed after all antihypertensive medications have been stopped.

4- A summary of symptoms will be provided to the subjects and/or their proxy. They will be asked to share this information with their spouses or other family members living in the same household or other close caregiver. They will be instructed to call the investigators immediately if any of these symptoms occur to arrange the transfer to the nearest emergency room. They will be provided with a pager number for the investigators. Weekly contact with the subject will be conducted by phone to obtain the blood pressure readings and review of any symptom that occurred.

5- The subjects will be asked to repeat the blood pressure measurement within 60 minutes if the reading is above 180/110 mm HG and call the investigators ( by phone or pager) anytime that they have two consecutive readings exceeding 180 mm Hg systolic or 110 mm Hg diastolic or have any unexpected discomfort, dizziness, or headaches. The study physician will then recommend based on the prior blood pressure readings and the participant symptoms to either alter the way the blood pressure medication is being reduced, take extra dose of the blood pressure medication, or resume all usual doses of all blood pressure medications immediately (the doses before the study) and continue measuring blood pressure as instructed. A failed taper is defined as persistent (>2 consecutive readings on 2 consecutive days) elevation in blood pressure >180/110 mm Hg. In the event that the participant failed the taper, the participant is asked to go back on their usual antihypertensive medications and is withdrawn form the study. The study personnel will contact the subject daily to obtain the blood pressure readings. This will continue until the blood pressure is back to the level before the medication reduction was started and they will be referred to their primary care physician for chronic blood pressure management. For their safety they will not be included in the study.

[figure not shown]

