## 4. SELECTION AND ENROLLMENT OF PARTICIPANTS

### 4.1. Inclusion Criteria

- (1) Age: 60 years or older;
- (2) Hypertension: SBP $\geq$ 140 mm Hg or DBP $\geq$  90 mm or receiving antihypertensive medications. Currently treated hypertensive individuals are eligible if they are willing to taper their medications. We will use a step-wise protocol of lowering antihypertensive medications;
- (3) Executive MCI will be defined using these criteria:

- (a) The Montreal Cognitive Assessment (MoCA) score less than or equal to 26: MoCA is a 30-point scale administered in 10 minutes, is validated in multiple languages and is highly sensitive to identify mild vascular-related cognitive dysfunction (sensitivity 90% and specificity 87%).
- (b) Executive dysfunction: A performance at the 10th percentile or below on at least one of four screening tests for executive function: Trail Making Test, Part B (TMT-B), modified Stroop interference, Digit Span and Digit Sequencing, and Letter fluency
- (c) Minimal Functional limitation as reflected by the Functional Assessment Questionnaire (FAQ)  $\leq 7$ .

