## 4.2 Exclusion Criteria

- (1) Intolerance to candesartan or lisinopril ;
- (2) SBP >200 or DBP >110 mm Hg;
- (3) Renal disease or hyperkalemia (SCr >1.99 mg/dl or K > 5.5 meq/dl);
- (4) Active medical or psychiatric problems (An active problem is one that requires medical attention and is deemed as a safety risk by the study physician, for example current cancer treatment, infections such as pneumonia, current gastrointestinal or other internal bleeding, HIV treatment, hematological disease, Parkinson's disease, multiple sclerosis)
- (5) Uncontrolled congestive heart failure [shortness of breath at rest or evidence of pulmonary edema on exam];
- (6) History of stroke in the past 3 years (self-reported clinical stroke within the past 3 years/ incidental infarcts on MRI scanning is allowed);
- (7) Inability to perform the study procedures (those with contraindications for MRI will be enrolled but will not undergo the MRI; those with history of asthma, COPD, or significant pulmonary disease will not undergo the CO2-reactivity protocol);
- (8) Women of childbearing potential
- (9) Current use of acetylcholine-esterase inhibitors or NMDA receptor antagonist (memantine) or a diagnosis of dementia self-report or care-giver report
- (10) In those who lack decision capacity, a *study surrogate* who can sign on their behalf will be required. Since we are enrolling only those with MCI, we anticipate that most participants will have decision capacity
- (11) Current use of Lithium, as most antihypertensive classes may lead to increased lithium toxic levels.

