### **5.3 Concomitant Interventions**

The goal of the trial intervention is to achieve a blood pressure <140/90 mm Hg in at least 90% of the participants. To achieve blood pressure control, we will use a stepwise protocol as follows: candesartan 8 mg→16 mg→32 mg or lisinopril 10 mg→20 mg→40 mg. Both groups will also receive, if needed to achieve blood pressure control, HCTZ 12.5 mg→25 mg, Amlodipine 2.5 mg →5 mg→10 mg and metoprolol 12.5 mg→25 mg (extended release)→50 mg (extended release). Antihypertensive medications will be increased every 2 weeks until blood pressure control (less than 140/90 mm Hg) is achieved. Based on our prior study, we anticipate being able to achieve blood pressure control within 4-8 weeks in the majority of the participants. Only the candesartan and lisinopril treatments are blinded. The remaining treatments (HCTZ, Amlodipine, and Metoprolol) are open-label. In the instance where a participant cannot receive an add-on agent, e.g. if there is a history of allergy or intolerance to one of the add-on drugs (HCTZ, Amlodipine, and Metoprolol) or a contraindication due to drug-drug interaction (e.g. simvastatin dose >20 mg and amlodipine), then that add-on agent will be skipped and the next add-on drug will be used.

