## **5.6 Prohibited Interventions**

Once participants are enrolled, addition of antihypertensive medications by non-study providers is not allowed. However, non-hypertensive medications are allowed as part of usual care. If a subject receives an antihypertensive medication from a non-study source after enrollment, the study physician will attempt to contact the prescribing provider, as long as the participant agrees, to explain the study protocol and request that all antihypertensive medications be prescribed through the study physician. If the participant or the provider does not agree to these recommendations, the participant will be withdrawn from the study for safety reasons.

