# **6. EXPERIMENTAL PROCEDURES AND MEASURES**

## **6.1 Questionnaires and lifestyle and anthropometric measures**

Study interviews will be conducted in English as necessary and include the following:

(1) Demographic, social and medical history data, as well as a medication inventory will be collected. All participants are asked to bring all their prescribed medication bottles. The medication inventory will be done by inspecting the participant medication and recording the name, dose, frequency and indication if known.

(2) Instrumental activities of daily living (IADL) scale .

(3) We will specifically evaluate functional abilities related to the executive cognitive function using the Dysexecutive Functioning Questionnaire (DEX). DEX is a 20-item questionnaire, which is completed by the participant and study partner and is designed to assess everyday signs of executive difficulties.

(4) Weight and height (stadiometer to measure height with the subjects standing and balance beam scale to measure weight without shoes).

(5) Short Physical Performance Battery [SPPB: ability to stand with the feet side-by-side, semi-tandem, and tandem, time to walk 8 feet (measured twice), and time to rise from a chair and return to the seated position 5 times) which assesses balance, gait, strength of the lower extremities, and endurance in older persons];

(6) Physical activity will be assessed using the Physical Activity Scale for the Elderly (PASE), which measures occupational, household, and leisure activities during a one-week period and has high reliability in older adults.

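### The pre-baseline taper in 8.3 has no exception by indication, so unless the study physician steps in, a participant with stable heart disease can be taken off a drug that treats the heart

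*Combined protocol and SAP*

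**What the plan says.** **Entry.** Section 4.1(2) states: "Currently treated hypertensive individuals are eligible if they are willing to taper their medications". No condition is attached about why the drug was prescribed. Section 4.2(5) excludes "Uncontrolled congestive heart failure [shortness of breath at rest or evidence of pulmonary edema on exam"; stable heart failure, angina, prior MI and arrhythmia are not named. Section 4.2(4) excludes active medical problems, defined as follows: "An active problem is one that requires medical attention and is deemed as a safety risk by the study physician". None of its examples is cardiac.

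**Taper.** Section 8.3 states: "Once the participant is off all antihypertensive medications, he or she will undergo the baseline evaluation". Step 3 of the same section says again that baseline follows the stopping of all such drugs. The taper table is organised by number of drugs, not by what they treat. A failed taper is defined by blood pressure alone.

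**After randomisation.** Section 5.3 conditions the add-ons on blood pressure: "Both groups will also receive, if needed to achieve blood pressure control, HCTZ", then amlodipine, then metoprolol. Section 8.2 lets the study physician adjust drugs at discretion for safety. Under 5.6, "addition of antihypertensive medications by non-study providers is not allowed" once a participant is enrolled. An outside prescription has to be routed through the study physician, or the participant is withdrawn.

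**Information available.** The medication inventory in 6.1 involves "recording the name, dose, frequency and indication if known", and Table 2 schedules it at screening. No eligibility or taper rule uses that field.

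**The concern.** Many antihypertensives have a second job. A beta blocker may be controlling angina or heart rate, and a diuretic may be keeping heart failure stable. The plan treats them all as blood pressure drugs to be cleared before baseline. Section 8.1 itself names cardiac symptoms and chest pain among the risks of stopping treatment.

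If the protocol is followed as written and nobody acts on the indication, a participant could go without a cardiac drug through the taper. If blood pressure is controlled without it, the gap could last for the rest of the treatment year. The protocol does write explicit rules for other foreseeable hazards, such as lithium, simvastatin with amlodipine, and CO2 inhalation in asthma or COPD. It has none for this one. What is at stake is participant safety.

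**Working it through.** The plan states no figure on this point, so the check is mainly a reading of the sections in sequence, with three small calculations.

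**1. Following one participant through the text.** Take someone with stable angina on a beta blocker.
- 4.1(2): eligible if willing to taper.
- 4.2(5): does not apply. 4.2(4): applies only if the study physician regards the angina as an active problem and a safety risk.
- 8.3: the beta blocker is tapered to zero before baseline. Readings persistently above 180/110 mm Hg fail the taper; there is no cardiac criterion.
- 5.3: doses rise every 2 weeks until control. The listed order has 3 study-drug steps, 2 HCTZ steps and 3 amlodipine steps before metoprolol: 3 + 2 + 3 = 8. Assuming strict order, with step 1 at week 0, metoprolol is step 9 and starts at (9 - 1) x 2 = week 16. If HCTZ and amlodipine are both skipped it is step 4, at (4 - 1) x 2 = week 6. If blood pressure is controlled first, it does not start. Section 5.3 expects control within 4-8 weeks in most participants.
- Section 9 lists new MI and symptomatic dysrhythmia as reasons to discontinue, but these act after the event.

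**2. Time off drug before study treatment (8.3 taper table, three-drug row).**
- First drug tapered: off from day 8, baseline on days 22-28. Gap: 22 - 8 = 14 to 28 - 8 = 20 days.
- Last drug tapered: half dose through day 21, off from day 22. Gap: at most 28 - 22 = 6 days, consistent with the 7.1 visit window of no more than 1 week off treatment.

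The table fixes no order among drugs, so either end is possible.

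**3. Number affected.** The documents give no prevalence of cardiac indications. Each 1% of the 160 enrolled is 160 x 0.01 = 1.6 participants.

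**4. Screening cost of an exclusion (10.6).** The inputs are 332 screened, 55% eligible, 160 enrolled, 140 final and dropout of 10-15%.
- Eligibility alone gives 332 x 0.55 = 182.6 eligible, which is more than 160.
- Adding a 12.5% loss (the midpoint of 10-15%) gives 160 / (0.55 x 0.875) = 332.5, which reproduces the stated 332. Also 140 / 0.875 = 160. So the gap between about 183 and 160 looks like an attrition allowance, although 10.6 does not show its arithmetic.
- With 15% of eligible people excluded (assumption):
  - if the gap were truly spare, 160 / (0.55 x 0.85) = 342.2, so 343 screened, 11 more;
  - if the 12.5% loss occurs, 160 / (0.55 x 0.875 x 0.85) = 391.1, so 392 screened, 60 more.

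**The case against.** The case for leaving the plan alone has four parts.

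**Exclusion 4 is wider than acute illness.** Its examples are illustrative and include HIV treatment, Parkinson's disease and multiple sclerosis, all chronic. Treated angina, heart failure or arrhythmia could fall under it. Screening already includes history, examination and medication review before the taper. This stands in part: a careful physician may catch many cases. But the criterion is discretionary, and a patient who is stable because of the drug may not look active. Because 4.2(5) limits heart failure to the uncontrolled form, staff could reasonably read stable disease as eligible.

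**The text is silent on dual-purpose drugs rather than hostile to them.** Section 5.4 continues usual care and 5.6 permits drugs not given for hypertension. A reader might infer that 8.3 orders heart drugs to be stopped whatever their purpose. It does not say that; a beta blocker recorded as an arrhythmia treatment could be read as usual care. Equally, nothing says that it should be kept, so the outcome depends on who reads the protocol.

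**Monitoring is substantial.** Section 8.3 provides weekly contact, home readings, a symptom list, a pager number, emergency transfer and physician discretion to change the taper or resume all drugs. The primary care provider is notified if the participant agrees. These are real protections, but apart from the conditional notice they respond to symptoms or high readings.

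**Prior experience was clean.** Section 2.3 reports 53 people tapered without symptoms. It does not say whether any took a drug for a cardiac indication, and 0 of 53 is compatible with a rate up to 1 - 0.05^(1/53) = 5.5% (one-sided 95% bound).

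**Conclusion.** The gap is real: no indication-based rule operates before the taper, and loss of a cardiac drug is prevented only if the physician or another clinician acts. It merits a protocol change on safety grounds. Its size in participants cannot be stated. The week-16 figure assumes strict step order, and the full-year gap further requires that neither the study physician nor usual care responds to the indication.

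Three stronger readings are not supported:
- **That the arm comparison is biased.** The taper precedes randomisation and is the same for both arms.
- **That up to 1 - 160/182.6 = 12.4% of eligible people could be excluded at no cost.** The stated 332 appears already to contain a loss of about 12.5%, so no free margin should be claimed.
- **That people taking an ACE inhibitor or ARB for the heart are exposed in the same way.** Both arms start a drug of one of these two classes after baseline, so they face a short interruption, not a long-term loss.

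**What to change.** Use the indication recorded in the screening medication inventory, confirmed with the prescriber where the participant agrees, and act on it before any taper. Then choose one of the following.

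- **(a) Exclude.** Add to 4.2 anyone taking a non-renin-angiotensin antihypertensive for heart failure, angina, prior MI or arrhythmia.
- **(b) Keep as background.** Continue that drug unchanged in both arms and taper only the rest. Write matching exceptions into 8.3 and 5.6. For an add-on of the same class, apply the existing 5.3 rule: "then that add-on agent will be skipped and the next add-on drug will be used".

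Participants whose only such drug is an ACE inhibitor or ARB need not be excluded automatically. Option (b) does not suit them, because the drug would duplicate study treatment; the study physician should judge and record whether the short interruption is safe.

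**Cost.** Option (a) shrinks the eligible pool by an unknown amount and makes the results apply less to hypertensive people with heart disease. At the assumed 15%, screening rises by 11 to 60 people. Option (b) keeps the pool, but baseline is not fully off drug for these participants and an add-on step may be lost for blood pressure control. The background drug is the same at baseline and 12 months and is balanced on average by randomisation.
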